3.4 Safety Objective

- To assess the safety and tolerability of miricorilant versus placebo.

3.5 Pharmacokinetic Objective

- To assess the PK of both dose levels of miricorilant.

4 STUDY ENDPOINTS

4.1 Primary Efficacy Endpoint

Relative change from Baseline to Week 12 in liver fat content assessed by magnetic resonance imaging-proton density fat fraction (MRI-PDFF) for both dose levels of miricorilant versus placebo.

4.2 Secondary Efficacy Endpoints

The following endpoints will be assessed relative to Baseline:

- Change in liver fat content assessed by MRI-PDFF for both dose levels of miricorilant combined versus placebo.
- Proportion of patients achieving a relative reduction in liver fat content of $\geq 30\%$ by MRI-PDFF for miricorilant versus placebo.
- Absolute change in liver fat content by MRI-PDFF for miricorilant versus placebo.
- Change in aspartate aminotransferase (AST), alanine aminotransferase (ALT), and gamma-glutamyl transferase (GGT) for miricorilant versus placebo.
- Change in propeptide of type III collagen (pro-C3) for miricorilant versus placebo.
- Change in enhanced liver fibrosis (ELF) score and its components (hyaluronic acid, tissue inhibitor of metalloproteinases-1 [TIMP-1], type III procollagen [PIINP]) for miricorilant versus placebo.

4.3 Exploratory Endpoints

The following endpoints will be assessed relative to Baseline:

- Proportion of patients achieving a relative reduction in liver fat content of $\geq 50\%$ by MRI-PDFF for miricorilant versus placebo.
- Proportion of patients with complete resolution of fatty liver by MRI-PDFF for miricorilant versus placebo.

In all patients:

- Changes in ACTH, serum cortisol, and serum aldosterone (pharmacodynamic assessments).

- Change in absolute body weight.
- Change in Homeostatic Model Assessment of Insulin Resistance (HOMA-IR).

In patients with diabetes:

- Change in HbA1c.
- Change in fasting blood glucose.

In patients with high blood pressure:

- Change in blood pressure.

4.4 Safety Endpoints

The following endpoints will be assessed for miricorilant versus placebo:

- Incidence of treatment-emergent adverse events (TEAEs), adverse events (AEs), and Serious TEAEs.
- Changes from Baseline in clinical laboratory tests (hematology and chemistry panels).
- Changes from Baseline in physical examinations and vital sign measurements.
- Changes from Baseline in electrocardiogram (ECG) parameters.

5 SAMPLE SIZE CONSIDERATIONS

The planned sample size is approximately 40 patients/group or approximately 120 subjects randomized 1:1:1 across 2 miricorilant treatment groups and one placebo group. The sample size calculation assumes that the standard deviation (SD) for change in liver fat content (LFC) due to treatment will be comparable to that observed in [Patel et al. 2016](#), where an SD of 33% was reported, and in [Harrison et al. 2019](#), where the SD was not reported but can be estimated from confidence intervals to be about 28%. A slightly more conservative estimate of 35% is assumed for the calculation here. Assuming that placebo patients experience a reduction in LFC of 10%, 34 patients per group affords 80% power to detect a significant difference at the $\alpha=0.05$ level between either miricorilant dose group and placebo as long as the miricorilant group achieves a 35% or greater reduction in LFC. Assuming that up to 10% of patients may drop out prior to the Week 12 MRI-PDFF assessment, the required sample size increases to 38 patients per group or 114 total patients. The sample size has been rounded up to 40 patients per group, or 120 total patients, for convenience. The sample size estimate has not been adjusted for multiple comparisons.

6 ANALYSIS POPULATIONS**6.1 All Enrolled Population**

The All Enrolled population comprises all patients who meet study enrollment criteria.

6.2 Safety Population

The Safety population comprises all patients who receive at least 1 dose of study medication. Safety data such as AEs will be summarized based on the Safety population.

6.3 Intent-To-Treat (ITT) Population

The ITT population comprises all patients who are randomized to the study. Efficacy data will be summarized based on the ITT population.

7 DEFINITIONS, COMPUTATIONS AND CONVENTIONS

The statistical principles applied in the design and planned analyses of this study are consistent with [International Council for Harmonisation \(ICH\) E9 guidelines \(ICH 1998\)](#). All statistical analyses detailed in this SAP will be conducted using SAS version 9.4 or higher.

7.1 Definitions

Study day for efficacy will be calculated in reference to the date of first dose of miricorilant or placebo (Study Day 1). For assessments conducted on or after the first dose date, study day is calculated as (assessment date – first dose date + 1). For assessments conducted before the first dose date, study day is calculated as (assessment date – first dose date). There is no study Day 0.

Treatment-emergent period: The treatment-emergent period is defined as the period of time from the date of the first dose of study drug (inclusive) through 28 days after the last dose of study drug. The treatment-emergent period will be used in the summaries of TEAEs.

Baseline will be the assessment on the Day 1 visit if non-missing, or the last non-missing assessment prior to first dose of study drug if Day 1 visit is missing.

7.2 Reporting Conventions

Unless otherwise specified, the following conventions will be applied to all analyses:

- Mean, median, 25th percentile, and 75th percentile values will be formatted to 1 more decimal place than the measured value. Standard deviation values will be formatted to 2 more decimal places than the measured value; minimum and maximum values will be presented to the same number of decimal places as the measured value.
- Percentages will be rounded to 1 decimal place. Number and percentage values will be presented as xx (xx.x%).
- Listings will be sorted for presentation in order of patient identifier (ID), and date of procedure or event.
- Analysis and summary tables will have the analysis population sample size (i.e., number of patients).
- Laboratory data will be reported using Système International (SI) units
- For by-visit observed data analyses, percentages will be calculated based on the number of patients with non-missing data as the denominator unless otherwise specified.

- For other continuous endpoints, the summary statistics will include mean, standard deviation, median, 25th percentile, 75th percentile, and range (minimum and maximum).
- For categorical endpoints, the summary statistics will include frequency counts and percentages.
- Medical history and adverse events will be coded using the Medical Dictionary for Regulatory Activities (MedDRA v 23.0. Adverse event severity will be evaluated using the National Cancer Institute Common Terminology Criteria for Adverse Events (CTCAE v.5.0).
- Prior therapies and concomitant medications will be coded using the World Health Organization (WHO) Drug Dictionary and summarized by Anatomical Therapeutic Chemical (ATC) therapeutic subgroup and preferred drug names.
- For continuous values (clinical laboratory values) that are not able to be determined due to being less than the lower limit of quantification (LLOQ) or higher than the upper limit of quantification (ULOQ), the value will be assigned to one unit lower than the LLOQ or one unit higher than the ULOQ for any analyses performed. The original value will be displayed in any listings provided.

7.3 Conventions for Dates

Conventions for calculations with dates are as follows:

- Dates will be stored as numeric variables in the SAS analysis files and reported in DDMMYY YYYY format (i.e., the Date9. date format in SAS).
- Dates recorded in comment fields will not be imputed or reported in any specific format.
- Intervals that are presented in weeks will be transformed from days to weeks by using the following conversion formula, and rounding to 1 decimal place:
 - WEEKS = DAYS / 7
 - MONTHS = DAYS / 30.4375
 - YEARS = DAYS / 365.25

Detailed rules for imputation of missing/partially missing dates for adverse events and prior/concomitant medications/procedures are provided in [Section 12.1](#).

7.4 Treatment Group Presentation

Patient disposition, protocol deviations, demographics and baseline characteristics, medical history, prior medications and procedures, and efficacy data summaries will be presented by randomized treatment group. Unless otherwise specified, safety data summaries will be presented by the actual treatment received.

7.5 Handling of Missing Data

Unless stated otherwise, missing data will not be replaced with imputed values.

Missing dates or partially missing dates will be imputed conservatively for adverse events and prior/concomitant medications/procedures. Specific rules for handling of missing or partially

missing dates for date of birth, adverse events, and prior/concomitant medications/procedures are provided in [Section 12.1](#).

7.6 Analysis Visit Windows

In analysis of data summarized by study visit, unscheduled and early termination visits will be reassigned a study visit where data is scheduled for collection based on the actual days relative to the date of first dose ([Table 1](#)). If multiple visits fall in the analysis visit window, the one closest to the target day will be used. If two visits are equidistant to the target day, then the later visit will be used.

Table 1 Analysis Visit Windows for Assessments

Visit Name	Start Day	Target Day	End Day
Baseline	—	1	—
Week 2	2	15	22
Week 4	23	29	36
Week 6	37	43	50
Week 8	51	57	64
Week 10	65	71	78
Week 12	79	85	92
Follow-up	> Study day of last dose of study drug	Initial visit after end of treatment	
Additional Follow-up	> Study day of last dose of study drug	Second visit after end of treatment	

Note: Any unscheduled and early termination visits that occur after the last dose of study drug will be classified in the follow-up period.

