4.4 Early Patient Discontinuation or Withdrawal

In this study, patient “discontinuation” refers to early discontinuation of study treatment while remaining on study; that is, the patient may wish to stop treatment early but may agree to continue with study visits and/or assessments.

Early patient “withdrawal” refers either to patient withdrawal of consent to any further study participation or to an Investigator/Sponsor decision to permanently withdraw the patient and cessation of all study treatments, procedures, and assessments without further follow-up. If a patient wishes to withdraw consent to further participation in the study entirely, this should be clearly documented (1) in the patient’s medical record and signed by the Investigator and (2) in the clinical study database/electronic case report form (eCRF).

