4.4.1 Early Patient Discontinuation of Study Drug

Study drug may be discontinued in the event of any of the following occurrences:

- Unacceptable toxicity.
- The Investigator decides it is in the patient’s best interest to discontinue treatment and/or participation in the study. Reasons may include but are not limited to the following:
 - The patient requires prohibited medications.
 - The patient is not compliant with protocol requirements.
- Patient becomes pregnant.

If a patient discontinues early from study drug, that patient will complete an Early Termination (ET) visit at the time of the last dose of the study drug, or soon thereafter. The Follow-Up visit will be conducted 28±5 days after the last dose of the study drug. Investigators should encourage these patients to continue with all study visits and/or assessments per the patient’s original study schedule through Week 12 (end-of-treatment). If the Follow-Up visit coincides with any other study visit, the assessments performed at these visits will be combined. If a patient is unable to continue with all study visits, they will be encouraged to complete the end-of treatment Week 12 visit at the very least, in addition to the ET and Follow-Up visits. Patients who complete at least 6 weeks of treatment and subsequently discontinue will be eligible for evaluation of liver fat content by MRI-PDFF. The date when the patient discontinues the study drug and the reason for discontinuation must be recorded on the eCRF

For guidelines about temporary interruption of study drug, see Section 5.3.

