4.4.2 Early Patient Withdrawal from Study

A patient may be withdrawn early from the study for the following medical or administrative reasons:

- Withdrawal of consent.

- Noncompliance, including refusal of the study treatment and/or failure to adhere to the study requirements, as specified in protocol.
- Lost to follow-up (before a patient is determined to be lost to follow-up, reasonable efforts will be made to contact the patient and complete study termination procedures).
- Early termination of the study by the Sponsor.

The date the patient is withdrawn from the study and the primary reason for withdrawal must be recorded on the eCRF.

Patients may withdraw voluntarily from the study at any time. For patients who withdraw consent to participate in the study, every effort should be made to determine whether the withdrawal of consent was related to an AE or a specific aspect of the study. As noted above, if a patient wishes to withdraw consent to further participation in the study entirely, including follow-up, this should be clearly documented (1) in the patient's medical record and signed by the Investigator and (2) in the clinical study database (eCRF).

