2 STUDY OVERVIEW

2.1 Overall Design

This is a Phase 2a, randomized, double-blind, placebo-controlled study conducted in 120 patients with presumed NASH, based on blood tests and noninvasive measures, to evaluate the safety, tolerability, pharmacokinetics (PK), and preliminary efficacy of miricorilant.

[figure not shown]
The study consists of the following study periods:

- Screening Period: up to 6 weeks
- Treatment Period: Day 1 (Baseline) to Week 12
- Follow-up Period: 4 weeks after last study dose (Week 16)

Approximately 120 patients who are eligible for participation in the study will be randomized on Day 1 in a 1:1:1 ratio to 600 mg miricorilant, 900 mg miricorilant, or placebo, for 12 weeks of treatment. Randomization will be stratified by the presence or absence of diabetes.

Blood samples for the measurement of miricorilant plasma concentrations will be collected at the Week 6 visit according to the schedule of activities.

Figure 1 CORT118335-860 Study Design

Abbreviation: PK, pharmacokinetics; W, week.

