9.2 Patient Disposition

Screen failure information is collected in an interactive web response system (IWRS), not on the eCRF and it is not be incorporated into the Study Data Tabulation Model (SDTM) database. Information on participant screening will be presented in terms of the overall number of participants screened, number of patients who are screen failures, reasons for screen failures, and the number of participants in screening.

Participant disposition will show the number of patients who have been enrolled, in each analysis population, took study drug, discontinued treatment, discontinued from the study, reasons for discontinuations, completed 12 weeks of study treatment, completed the study, and completed the follow-up study visit.

Completion of the follow-up study visit is defined as completing the date of visit eCRF for the follow-up visit.

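### The SAP's Follow-up analysis visit is the first visit after the last dose, with no day range, so it can mix early post-dose values with 28-day values

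*SAP*

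**What the plan says.** SAP 7.6 assigns unscheduled and ET visits to analysis visits by days since first dose. The on-treatment rows of Table 1 each have a start day, a target day and an end day. The two post-treatment rows do not. Both start on any day after the last dose. The target for Follow-up is "Initial visit after end of treatment", and Additional Follow-up takes the second such visit. The Note to the table says: "Any unscheduled and early termination visits that occur after the last dose of study drug will be classified in the follow-up period".

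Protocol 4.4.1 describes two visits after early discontinuation. First, "that patient will complete an Early Termination (ET) visit at the time of the last dose of the study drug, or soon thereafter". Second, "The Follow-Up visit will be conducted 28±5 days after the last dose of the study drug". Protocol 7.4 and 7.5 list different assessments for the two visits.

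Elsewhere the SAP treats follow-up as the four-week visit. Section 2.1 places the follow-up period four weeks after the last dose. Section 9.2 states: "Completion of the follow-up study visit is defined as completing the date of visit eCRF for the follow-up visit".

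The laboratory, vital-sign and ECG summaries (SAP 9.9.3 to 9.9.5) are given by analysis visit, ending with Follow-up. SAP 9.8 records that the sponsor stopped the study early for safety reasons and that no patient reached Week 12.

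**The concern.** A reader of a by-visit safety table takes a row labelled Follow-up to show recovery about four weeks off drug. Table 1 defines it by visit order instead. Two patients with the same 28-day visit can appear in different rows because one had the ET visit on the last-dose day and the other had it the next day.

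This matters more than usual here. Because no patient reached Week 12, every patient who stopped drug did so early, and the protocol asks each of them for an ET visit. The rule could therefore affect most of the Follow-up row.

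Mixing need not be random. For suspected liver injury, Protocol Table 2 asks for repeat liver tests within 48 to 72 hours and then monitoring at least twice weekly. Patients with a liver signal are therefore the more likely ones to have extra visits soon after stopping.

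The label is also inconsistent across outputs. Disposition counts completion from the Follow-Up visit's own eCRF page, whereas the by-visit tables use the first post-dose visit. Protocol 4.4.2 lists "Early termination of the study by the Sponsor" as a reason for withdrawal, and 4.4 defines withdrawal as "cessation of all study treatments, procedures, and assessments without further follow-up". A patient with a post-dose ET and no 28-day visit would fill the Follow-up row without counting as having completed follow-up.

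**Working it through.** **Inputs.** The Table 1 rules and Note come from SAP 7.6. ET timing (at the last dose or soon after) and Follow-Up timing (28±5 days) come from Protocol 4.4.1. The last-dose day, the visit lags and the shares below are assumptions, because the documents give none.

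**Protocol window.** 28 − 5 = 23 and 28 + 5 = 33, so the Follow-Up visit falls at +23 to +33 days, a span of 10 days. A Table 1 Follow-up value can fall anywhere from +1 to +33, a span of 32 days.

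**Applying Table 1.** Assume the last dose is on Day 40. Sort the visits after Day 40; the first goes to Follow-up and the second to Additional Follow-up.

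| Post-dose pattern | Follow-up row | Additional Follow-up row |
|---|---|---|
| ET Day 40, Follow-Up Day 68 | +28 (ET goes to Week 6) | none |
| ET Day 41, Follow-Up Day 68 | +1 | +28 |
| ET Day 47, Follow-Up Day 68 | +7 | +28 |
| Unscheduled Day 43, ET Day 47, Follow-Up Day 68 | +3 | +7; the +28 visit has no row |
| No ET, Follow-Up Day 73 | +33 | none |

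Now count only the ET and Follow-Up visits, and combine ET lags of 0 to 7 days with Follow-Up lags of 23 to 33 days. The 28±5 visit is in Follow-up in 11 of 11 combinations at lag 0. It is in Additional Follow-up in all 7 × 11 = 77 combinations at lags 1 to 7.

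The rule for several visits in one window, which picks the visit closest to the target day, cannot help because the target here is not a day. An ET on Day 41 also fits both Week 6 (Days 37 to 50, counted from first dose) and, by the Note, follow-up.

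**Illustrative size.** Let a share p of the patients in the row have an ET at lag L, and let the rest have a visit at +28.

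- Mean days off drug = p × L + (1 − p) × 28
- SD = √(p(1 − p)) × (28 − L)

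| p | Mean, L = 1 | Mean, L = 7 | SD, L = 1 | SD, L = 7 |
|---|---|---|---|---|
| 0.2 | 22.6 | 23.8 | 10.8 | 8.4 |
| 0.5 | 14.5 | 17.5 | 13.5 | 10.5 |
| 0.8 | 6.4 | 11.2 | 10.8 | 8.4 |

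For example, with p = 0.5 and L = 1 the mean is 0.5 + 14 = 14.5 and the SD is 0.5 × 27 = 13.5. For comparison, if all visits were spread evenly over the 11 days from 23 to 33, the mean would be 28 and the SD √((11² − 1)/12) = √10 ≈ 3.2 days.

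**What happens to the displaced visit.** SAP 9.9.3 to 9.9.5 name Follow-up as the last summarised visit. It is unclear whether Additional Follow-up, which would then hold the 28-day value, is summarised at all.

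**A related case.** Protocol 7.4 schedules serum aldosterone at ET, and 7.5 does not schedule it at Follow-Up. SAP 9.8.3.6 nevertheless summarises it over treatment and follow-up. A post-dose ET aldosterone value would be labelled Follow-up, although none is scheduled there.

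**The case against.** The rule is pre-specified and has two post-treatment rows, which match the two visits asked of a patient who stops early. If every ET falls after the last dose, the rows separate ET from the 28-day visit cleanly. Analysis visits need not equal nominal visits, and SAP 9.2 gives its completion count an explicit definition of its own. The Note speaks of the follow-up period rather than the row, so the intent may have been to keep Follow-up for the eCRF visit. The blank end-day cells may be an effect of PDF reading. The documents give no ET timings, so no actual distortion is shown.

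The two-row defence fails because the rows follow visit order: an ET on the last-dose day and an ET one day later put the 28-day visit in different rows. The period reading does not rescue it either, because Table 1 then gives the first such visit to Follow-up. The missing end day is not needed for the argument; the target wording and the Note are enough.

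Three points do stand. The extent is unknown and could be close to nil: if all or none of the ETs fall after the last dose, and there are no other post-dose visits, there is little or no mixture. The sponsor-termination point shows only a possibility, since withdrawal read literally could remove the ET visit as well. The consequences are also contained. There are no between-group safety comparisons (SAP 9.9), and listings and the worst-value, shift, eDISH and last-post-baseline outputs do not use this row. Dated listings and the drug end date (SAP 9.7) let a reader work out time off drug.

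**Conclusion.** The concern holds and is minor. As written, Table 1 and its Note let one Follow-up row hold values from +1 to +33 days after the last dose, where the protocol's visit covers +23 to +33. The table does not show which values are which. A one-day difference in ET timing decides the row for the 28-day visit, and one extra unscheduled visit before a post-dose ET can leave that visit with no row.

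The rule follows directly from the text. The means and SDs of time off drug rest on assumed shares (20%, 50%, 80%) and assumed ET lags (1 and 7 days). They show what the rule permits and do not estimate what happened. No laboratory, vital-sign or ECG value has been shown to change. What is affected is the interpretation of descriptive by-visit rows in a study stopped for safety, where recovery off drug is a natural question.

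**What to change.** In SAP 7.6, define Follow-up as the visit closest to last dose plus 28 days, within a stated window around 28±5. Show post-dose ET visits in a separate row, with days since last dose and days on drug. Keep other post-dose visits in the listings and in the worst-value and last-value summaries. Applied to the five patterns above, this leaves only +28 or +33 in the Follow-up row. If Follow-up was meant to be only the eCRF Follow-Up visit, a sentence in 7.6 saying so would remove the ambiguity.

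The cost is SAP wording and a small change to the visit-derivation program, with no new data. There are two drawbacks. The by-visit tables gain a row, and that ET row pools exposures from 1 day to under 12 weeks, which is why days on drug should be shown. Patients with no visit inside the window would have no Follow-up value, so that row's n may fall. If outputs are already final, a table footnote and a deviation documented in the CSR, as SAP Section 1 provides, would be enough.
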